#### 3.1 Treatment Arms

This is a single arm study in which all participants will be changed to the study medication for a total of six months.

#### 3.2 Study Duration

Patients who satisfy inclusion criteria will be enrolled in the study during an initial period of up to 3 months. After initial enrollment and consent, patients will continue for a total of 6 months on the study drug.

### **4 STUDY PRODUCT INFORMATION**

4.1 Description

Ferric Citrate is known chemically as iron (+3), x (1, 2, 3-propanetricarboxylic acid, 2- hydroxy-), y (H2O) x=0.70 - 0.87, y = 1.9 - 3.3.

Ferric citrate's trade name is Auryxia. Auryxia 210 mg ferric iron tablets, equivalent to 1g ferric citrate, are film-coated, peach-colored, and oval-shaped tablets embossed with "KX52". The inactive ingredients are pregelatinized starch and calcium stearate. In addition, the film-coating contains the following inactive ingredients; hypromellose, titanium dioxide, triacetin, and FD&C Yellow #6/Sunset Yellow FCF Aluminum Lake, FD&C Red #40/Allura Red AC Aluminum Lake, and FD&C Blue #2/Indigo Carmine Aluminum Lake.

### **Mechanism of Action**

Ferric iron binds dietary phosphate in the GI tract and precipitates as ferric phosphate. Ferric phosphate is insoluble and is excreted out of the body in the stool. By binding phosphate in the GI tract and decreasing absorption, ferric citrate lowers the phosphate concentration in the serum.

4.2 Acquisition and Accountability

Ferric Citrate will be supplied by the manufacture, Keryx Biopharmaceuticals, Inc., in 200 tablet foil sealed bottles to the study site. This study is to be conducted at a single site, at LAMC, and the medication will be stored in a secure, locked location within LAMC campus pharmacy that is accessible only to the study investigators and staff. Medication will be

delivered every 2 months based on need. Participants will be able to keep any unused investigational product already dispensed at the termination of the study. Any medication that is unused or returned by participating patients will be properly disposed of with the aide of the study pharmacist per LAMC pharmacy's waste medication disposal protocol.

### 4.3 Formulation, Packaging, and Labeling

Auryxia, 210 mg ferric iron tablets equivalent to 1 g of ferric citrate are supplied as 200 tablets in 400-cc high-density polyethylene bottles.

### 4.4 Storage and Stability

Store at 20 to 25°C (68 to 77°F): excursions permitted to 15° to 30°C (59°F to 86°F) Protect from moisture.

### 4.5 Dosage, Preparation and Administration

Study medication will be dispensed in multiple of 200 tablet bottles on a monthly basis, based on a given participant's phosphorus binder requirement. Following the physician's monthly dialysis rounding, patient will be seen by the study coordinator on the same day, and the following month's supply of ferric citrate will be dispensed. In center hemodialysis patients will be asked to bring their study drug with them to the dialysis center, where they will undergo a weekly pill count. Peritoneal dialysis patients will have weekly telephone follow up by the study coordinator regarding medication compliance, and will have an in person monthly pill counting during their monthly dialysis follow up visit.

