### **PROTOCOL SUMMARY**

Title	Transition to Ferric Citrate among Hemodialysis and Peritoneal Dialysis Patients: A Phase 4 "Real World" Experience Study from Kaiser Permanente Southern California		
Short Title	FeCitrate		
Protocol Number	KP FeCitrate		
Study Phase	4		
Study Site(s)	Los Angeles Kaiser Sunset Medical Center		
Number of Subjects	55		
Study Arms	1		
Indication	Hyperphosphatemia in end stage renal disease		
Primary Purpose	To evaluate the efficacy of ferric citrate for control of serum phosphorus levels and maintenance of adequate iron stores among dialysis-dependent patients before and after conversion from traditional phosphate binders in a "real world" environment		
Overview of Study Design	prospective non-randomized cohort study of 6-9 months duration (active study period 6 months).		
Investigational Product Administration	One to two tablets of Ferric Citrate phosphorus binder administered by mouth before every meal to prevent dietary phosphorus absorption.		
Eligibility Criteria	
 
Inclusion criteria:
 
On 3 + per day of calcium acetate, sevelamer, lanthanum, aluminum, or calcium carbonate
 
Mean serum phosphorus 4.0-<8.0 mg/dl for the past 6 months
 
No allergy to iron
 
Mean corrected calcium >8.0mg/dl for past 6 months
 
		
	
 
Mean PTH < 1000 pg/ml for past 6 months
 
		

	• Mean ferritin < 1500 ng/ml and mean iron sat < 50% for past 6	
	months	
	Patients with diabetes will be included	
	Exclusion criteria	
	History of gastrointestinal bleeding within past 6 months	
	History of hospitalization for gastroparesis, bowel obstruction,	
	or abdominal surgery within past 6 months	
	Active malignancy	
	Renal transplant	
	History of autoimmune disease, hemoglobinopathy,	
	hemochromatosis, or sickle cell disease	
Study Endpoint	Mean serum phosphorus levels and rate of successful phosphorus control (<5.5mg/dl) 6 months before and after treatment with ferric citrate	
Statistical Methods	Not powered to detect statistical significance	

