Circulatory function is further compromised by declining hemoglobin levels and anemia in the CKD population. The insufficient erythropoiesis that occurs as renal function declines likely compounds the vascular pathology that occurs in the setting of CKD-MB. In addition, elevated serum phosphorus levels and associated hyperparathyroidism lead to bone marrow suppression, compounding the anemia. Erythropoiesis stimulating agents (ESA's) are a routine part of management of patients with CKD/ESRD, but are not without adverse effects, including an increased risk of cardiovascular events, mortality, and malignancy. Current recommendations regarding use of ESA's in ESRD patients are to use the minimum dose required to prevent blood transfusion. Maintenance of adequate iron stores ensures adequate erythropoiesis and avoids excessive use of ESA's.

Control of serum phosphorus levels can be a challenge for patients with ESRD and depends largely on patient adherence to diet and phosphate binder use. Many patients have difficulty tolerating binders, possibly due to pill size and high pill burden(14, 15). It is not unusual for ESRD patients to consume upwards of 10 pills per day in an effort to control serum phosphorus levels. Simpler medication regimens for phosphorus control would likely result in improved compliance and better outcomes for patients with ESRD.

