### **3 STUDY DESIGN**

- Type: non-randomized, single arm, phase IV, cohort pilot study
- Study population: end stage renal disease patients who are on chronic hemodialysis or peritoneal dialysis with elevated serum phosphorus.
- 55 chronic dialysis patients (28 hemodialysis and 27 peritoneal dialysis) who are currently using oral phosphorus binders will be enrolled. Potential participants will be screened from both the chronic hemodialysis unit and the home dialysis unit at the LAMC site. Potential study patients will be approached by study investigators during any routine visit. If the patient consents to participation, the study coordinator will see patients during the same visit. If study staff is unable to meet with patient during routine visit or if the patient requests more time to consider participation, peritoneal dialysis patients may be asked to return to clinic for an additional visit to sign the informed consent. This will only apply to peritoneal dialysis patients. If the patient chooses not to enter the study, the reason will be noted by the study coordinator. At the appropriate time in the study, the study coordinator will dispense the study medication, Ferric Citrate, and provide instructions per study protocol. The study coordinator will meet with the participant every month during either a hemodialysis visit (for hemodialysis patients) or a monthly clinic visit (for peritoneal dialysis patients) with his/her provider, and laboratory values/data and study questionnaire will be updated each month. If at any time during the study, a peritoneal, dialysis patient changes to hemodialysis, the patient can continue study at the principal investigator's discretion. If at any time during the study, a hemodialysis patient changes dialysis to peritoneal, the patient can continue on study at the principal investigator's discretion. In such event, patient's group assignment for analysis will be determined at the discretion of the Principal Investigator. Patients will be allowed to continue in the trial given that they can continue to meet all study participation requirements. The six month period prior to enrollment will be used to evaluate the

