7.2 Criteria for Removal from Treatment

7.2. 1 After six months of study drug use, the study drug will no longer be provided by Keryx free of charge. Patients may continue with Ferric Citrate as their oral phosphorus binder of choice, if desired (at their own expense).

7.2.2 Patients will discontinue treatment in the event of iron overload or any serious adverse side effect deemed attributable or possibly attributable to the study drug.

7.2.3 Patient will be removed if he/she misses the medication continuously for more than 2 weeks.

7.2.4 A patient will be removed from treatment if he/she receives a renal transplant.

7.2.5 Patient will be removed from the study if consent is withdrawn or patient is lost to follow up.

7.2.6 At the discretion of the principal investigator, a patient may be removed from study if they initiate dialysis care at an outside/Non-Kaiser Permanente facility.

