### 9.1.2 Recording of baseline data

A baseline assessment of patient's compliance with usual medications will be performed.

The study coordinator will then review previously obtained routine monthly laboratory values from the dialysis unit, including complete blood count, iron saturation, ferritin, phosphorus, calcium, parathyroid hormone (a total of 6 months of previous data to be reviewed). The study coordinator will then use this baseline data to help determine a patient's eligibility for participation in the active portion of the study, based on the criteria listed in section 5.1. After it is determined that patient actually qualifies for participation in the study, the following will be recorded by the study coordinator:

- Patient's average weekly IV iron and erythropoiesis stimulating agent use (6 months of retrospective data)
- 6 months of retrospective routine laboratory data (CBC, iron saturation, ferritin, calcium, phosphorus, albumin, intact parathyroid hormone levels) will be recorded for each of the previous 6 calendar months
- 6 months of retrospective data regarding medication use will be recorded for each of the previous 6 calendar months (including calcitriol or other vitamin D analogs, cinacalcet, and phosphorus binders), including frequency and dose

After baseline data is obtained, participants will be dispensed a 1 month supply of the study medication, with the starting dose of 1-2 tablets per meal, three times a day. This will mark the start of the active study drug phase.

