### **10 CRITERIA FOR EVALUATION AND ENDPOINT DEFINITIONS**

### 10.1 Primary Endpoints

Mean serum phosphorus levels and rate of control (<5.5mg/dl) 6 months before and after treatment with ferric citrate, including PTH, calcium, iron saturation, ferritin, hemoglobin and aluminum levels

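### Adherence support, early titration and a missed-drug removal rule all start with ferric citrate, so the before/after change measures conversion under that support and not real-world efficacy of the drug

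*Combined protocol and SAP*

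**What the plan says.** Section 3 describes a "non-randomized, single arm, phase IV, cohort pilot study". The primary endpoint in section 10.1 is "Mean serum phosphorus levels and rate of control (<5.5mg/dl) 6 months before and after treatment with ferric citrate". The Protocol Summary states the purpose as evaluating efficacy "before and after conversion from traditional phosphate binders in a 'real world' environment". In section 2, aim 1 is efficacy and tolerability, and aim 2 compares ferric citrate with calcium acetate and sevelamer carbonate.

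Section 9.1.2 makes the first dispensing the start of the active phase. From that point:

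- Hemodialysis patients bring their drug to the center, "where they will undergo a weekly pill count" (section 4.5).
- Peritoneal dialysis patients have a monthly in-person pill count and compliance calls. The calls are weekly in section 4.5 and bi-monthly in section 9.1.5 (in-center and home follow-up).
- Section 7.1 sets labs every two weeks for two months and allows titration at that interval.
- Section 7.2.3 says: "Patient will be removed if he/she misses the medication continuously for more than 2 weeks".
- Drug is supplied by the study. After six months "the study drug will no longer be provided by Keryx free of charge" (section 7.2.1).

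For the earlier six months, section 9.1.2 uses routine monthly labs and recorded binder frequency and dose. On adherence it says only that an assessment of the patient's "compliance with usual medications will be performed". Section 14.4, the final analysis plan, is marked not applicable.

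**The concern.** Section 1.1 says that control of phosphorus "depends largely on patient adherence to diet and phosphate binder use". A design that steps up adherence monitoring at the moment of the switch, with no concurrent group, cannot separate the drug from the monitoring. Both primary phosphorus measures, the mean and the rate below 5.5 mg/dl, are affected.

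Adherence is also measured differently in the two periods: one baseline assessment with no stated method, against repeated pill counts. The third secondary endpoint, pills per day against the previous pill burden, may therefore set recorded use against counted use.

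At stake is what may be concluded. The earlier period is usual care and the later one is monitored care, yet the purpose describes the contrast as drug efficacy in ordinary practice.

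**Working it through.** The plan gives no effect size, standard deviation, alpha or power, so there is no figure to reproduce. The only check available is 28 + 27 = 55, which agrees.

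**Step 1. The two periods side by side** (six months taken as 26 weeks)

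| Element | Six months before | Six months on ferric citrate |
|---|---|---|
| Hemodialysis pill counts | none described | about 26 (4.5) |
| Peritoneal dialysis compliance calls | none described | about 26 if weekly (4.5); under the bi-monthly wording (9.1.5), about 12 if twice a month or 3 if every two months |
| Peritoneal dialysis pill counts | none described | about 6 |
| Phosphorus draws | 6 monthly | 4 + 4 = 8 (7.1), or 7 if the optional week-6 draw in 9.1.4 is skipped |
| Removal for missed drug | none described | after more than 2 weeks (7.2.3) |
| Adherence measure | one assessment, method not stated | repeated pill counts |

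The lab difference is small: 8/6 − 1 = 33% more draws, or 7/6 − 1 = 17%, all within the first two months. The pill counts and calls continue throughout. The removal rule works differently from support: it can take non-adherent stretches out of the later data, with no counterpart in the earlier data.

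**Step 2. Illustrative size.** Every input here is an assumption. Suppose both drugs are equally effective when fully taken, and all of the adherence rise comes from the support. Then:

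fall in mean phosphorus = rise in adherence × effect of a fully taken binder

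- Set A (rise of 15 to 25 points, effect 1.0 to 2.5 mg/dl): 0.15 × 1.0 = 0.15, up to 0.25 × 2.5 = 0.625 mg/dl.
- Set B (rise of 10 to 30 points, effect 1.5 to 3.0 mg/dl): 0.10 × 1.5 = 0.15, up to 0.30 × 3.0 = 0.90 mg/dl.

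**Step 3. Against the precision of the study.** The 95% half-width for a paired mean is t(54, 0.975)/√55 = 0.270 SD. For an assumed SD of change of 0.8 to 1.5 mg/dl this is 0.270 × 0.8 = 0.22 to 0.270 × 1.5 = 0.41 mg/dl. A 0.15 fall lies inside that margin; the upper values lie outside it.

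If a paired two-sided 5% test were run, its chance of significance under a fall d is Φ(d/SE − 1.96) + Φ(−d/SE − 1.96), with SE = SD/√55. With no drug difference and SD from 1.5 down to 1.0, this is 12% to 20% for d = 0.15 and 51% to 84% for d = 0.40.

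**Step 4. The control rate.** If patient means are normal with mean 5.8 and SD 1.0 mg/dl (assumed), the rate below 5.5 is Φ(−0.3) = 38%. After a 0.40 fall it is Φ(0.1) = 54%.

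More patients would narrow the interval but leave this component unchanged.

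**The case against.** The strongest reply is that this is an openly uncontrolled pilot. The Protocol Summary says it is not powered, section 14 gives feasibility as the goal, and section 14.1 hypothesizes successful transition. No report exists in which efficacy has been claimed. That stands as far as it goes, but the Summary and section 2 do state efficacy, and lack of power concerns precision, not this confounding. The 30-day follow-up labs do not help, because scheduled support and study supply end with the study.

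Several stronger readings are tempting, and the documents do not support them:

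- *The net bias favors ferric citrate.* Support probably does. But section 7.1 converts two or more tablets of most binders to the same starting dose and titrates upward, so a patient who had been on many tablets starts on fewer. That could work the other way early in the averaged period.
- *All of any adherence gain is spurious.* Section 1.1 expects simpler regimens to improve compliance, so part of a gain could belong to the drug. Step 2 credits none of it to the drug.
- *Patients' costs fell at the switch.* Study drug is free, but nothing states what patients paid before.
- *Previous adherence is ignored.* Section 9.1.2 plans an assessment and six months of recorded dose and frequency. The absence of a baseline mark in the section 9.4 compliance row is weak evidence, because that row is for updates. The gap is the unstated method.
- *Titration is more intensive throughout.* The extra draws number one or two.

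**Conclusion.** The point holds in a limited form. Coordinator support, early extra labs with two-weekly titration, and the removal rule begin with the drug and are not described for the comparison period. The phosphorus change is therefore an estimate for conversion to study-supplied ferric citrate under that support. It does not establish efficacy of the drug alone, and the later period is not ordinary care.

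This conclusion rests on the protocol's text and needs no numerical assumption. The size does: 0.15 to 0.90 mg/dl shows what is possible and is not an estimate of the bias. Net direction is not established. A reader might infer that the study is uninformative. That goes too far: a descriptive account of switching under these conditions remains useful. Attribution to the drug would need the same support on the old binder, through a prospective run-in or a concurrent group.

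**What to change.** (a) In the Protocol Summary and section 2, restate the purpose and the permitted conclusion as the change in phosphorus after conversion to study-supplied ferric citrate with coordinator adherence monitoring. Do not attribute the change to the drug alone or call it real-world efficacy without qualification.

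(b) In section 9.1.2 and the section 9.4 calendar, define baseline adherence as previous-binder tablets dispensed divided by tablets prescribed over the same six months, from health-system records (availability assumed). For ferric citrate, use the planned pill counts: dispensed less remaining at each count, divided by prescribed. Report both descriptively beside the phosphorus change, and say that the two measures are not identical.

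A ferric citrate ratio based on returned tablets would not work. Supply is in 200-tablet bottles (section 4.5), participants may keep unused drug (section 4.2), and the final visit collects it only from those who withdrew. With nothing returned, one bottle in a 30-day month gives 200/90 = 2.2 at 3 tablets a day and 200/180 = 1.1 at 6 a day.

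Do not add a subset of patients whose adherence stayed stable: that conditions on something measured after the switch and possibly caused by the drug.

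(c) Reconcile sections 4.5 and 9.1.5 on the frequency of peritoneal dialysis calls before the support is described in any conclusion.

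Cost: a record pull for 55 patients, one table and a less favorable conclusion. If the records prove unavailable, (a) still costs only wording.

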4.6 Toxicity and Safety Information

Patients with iron overload syndromes (e.g., hemochromatosis) are contraindicated to take Ferric Citrate, as the iron absorption may lead to excessive elevation in iron stores. Iron levels in blood will be monitored closely on a monthly basis. Accidental overdose of iron-containing products is a leading cause of fatal poisoning in children under 6 years of age, therefore no children are included in this study. Patients with inflammatory bowel disease or active, symptomatic gastrointestinal bleeding were excluded from clinical trials, therefore these populations are excluded from this current study.

In clinical trials, adverse events reported in more than 5% of patients treated with Ferric Citrate, at a rate similar to the control group. Side effects reported included diarrhea (21%), nausea (11%), constipation (8%), vomiting (7%), and cough (6%4) as per the package insert. Gastrointestinal adverse reactions were the most common reason for discontinuing Ferric Citrate. The study medication is also associated with discolored feces.

### 4.7 Concomitant Medications/ Treatments

Other non-study oral phosphorus binders are excluded from concomitant medications/treatments for the study due to potential impact on serum phosphorus and calcium levels. All other concurrent treatments are allowed.

Page 16 of 35

### **5** SELECTION AND WITHDRAWAL OF PATIENTS

#### 5.1 Inclusion Criteria

- 5.1.1 Currently using 3 + pills per day of calcium acetate, sevelamer, lanthanum, or calcium carbonate
- 5.1.2 Mean serum phosphorus 4.0-<8.0 mg/dl for 6 months prior to enrollment
- 5.1.3 No allergy to iron
- 5.1.4 Mean corrected serum calcium > 8.0 mg/dl for 6 months prior to enrollment
- 5.1.5 Mean PTH < 1000 pg/ml for 6 months prior to enrollment
- 5.1.6 Mean ferritin < 1500 ng/ml and mean iron sat < 50% for 6 months prior to enrollment
- 5.2 Exclusion Criteria
  - 5.2.1 History of gastrointestinal bleeding within past 6 months
  - 5.2.2 History of hospitalization for gastroparesis, bowel obstruction, or abdominal surgery within past 6 months
  - 5.2.3 Acute kidney injury equal to or less than 3 months before the initial screening date
  - 5.2.4 Active malignancy
  - 5.2.5 Functioning renal transplant
  - 5.2.6 Patients with iron overload syndrome (e.g., Hemochromatosis)
  - 5.2.7 History autoimmune disease, hemoglobinopathy, hemochromatosis, sickle cell disease
  - 5.2.8 Active or past history of calciphylaxis

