### **2 OBJECTIVES AND PURPOSE**

### SPECIFIC AIMS

 To determine efficacy and tolerability of ferric citrate in dialysis-dependent patients treated for hyperphosphatemia

Protocol Version 1.4, dated 26-Jun-2018

Page 13 of 35

- 2) To compare dose efficacy of ferric citrate to calcium acetate and sevelamer carbonate for control of serum phosphorus levels
- To determine changes in iron saturation and ferritin after conversion to ferric citrate
- 4) To determine iron requirements after conversion to ferric citrate
- 5) To determine changes in hemoglobin after conversion to ferric citrate
- 6) To determine ESA doses and requirements after conversion to ferric citrate

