participants' baseline laboratory values and medication use, including phosphorus binder use. Laboratory values and medication use will also be evaluated and recorded monthly during the six months of active study. The duration of the study will be six months on ferric citrate. At the end of the study, the participant can be provided with a prescription of ferric citrate by his/her nephrologist if the participant wishes to continue with ferric citrate, or he/she can go back to the phosphorus binder used before enrolling in this study.

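### Entry needs only current binder use, but the primary 'before' value is a fixed six-month mean, so months before a recent binder start count as previous-binder control

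*Combined protocol and SAP*

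**What the plan says.** Section 5.1 sets the binder criterion as "Currently using 3 + pills per day of calcium acetate, sevelamer, lanthanum, or calcium carbonate". No section adds a minimum duration, a stable dose, or a requirement that the same binder was used throughout a run-in. The laboratory criteria beside it do carry a window. Phosphorus, for example, is "Mean serum phosphorus 4.0-<8.0 mg/dl for 6 months prior to enrollment", and 5.1.4 to 5.1.6 average calcium, PTH, ferritin and iron saturation over the same period.

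Section 3 uses the six months before enrollment to establish "participants' baseline laboratory values and medication use, including phosphorus binder use". The primary endpoint in 10.1 is "Mean serum phosphorus levels and rate of control (<5.5mg/dl) 6 months before and after treatment with ferric citrate". The Protocol Summary describes the purpose as a comparison "before and after conversion from traditional phosphate binders", and the second specific aim is "To compare dose efficacy of ferric citrate to calcium acetate and sevelamer carbonate for control of serum phosphorus levels". The 'before' period is thus meant to show control on the earlier binder.

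Section 9.1.2 provides that "6 months of retrospective data regarding medication use will be recorded for each of the previous 6 calendar months", and the record includes phosphorus binders with frequency and dose. No endpoint definition uses this record to select or weight the 'before' months, and section 14.4 (Final Analysis Plan) is marked N/A.

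**The concern.** The entry rule looks at one point in time, while the comparator looks back six months. A patient who began a binder two months before enrollment satisfies 5.1.1, yet four of that patient's six 'before' months had no binder. Those months enter the 'before' mean and control rate as if they described the binder being replaced.

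Months with no binder are expected to show higher phosphorus. If so, part of the improvement produced by starting the first binder appears in the before/after difference and is credited to ferric citrate. The study has one arm and no concurrent control, so nothing in the design removes this. It affects the primary endpoint directly, and it remains whether or not a significance test is done.

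**Working it through.** **Plan's own figures.** The plan gives no alpha, power, effect size or standard deviation. The only figure that can be checked is enrollment: 28 hemodialysis + 27 peritoneal dialysis = 55, which agrees.

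**Inputs.** From the documents: a window of 6 months, a control threshold of 5.5 mg/dl, and an entry range for mean phosphorus of 4.0 to below 8.0 mg/dl. Assumed, because the documents do not give them: f, the share of patients who started a binder inside the window; m, the number of binder months those patients have; and d, the fall in phosphorus from starting the binder.

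**Shift in the group 'before' mean** relative to the on-binder level = f × (6 − m)/6 × d:

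| f | m | d (mg/dl) | Shift (mg/dl) |
|---|---|---|---|
| 10% | 4 | 1.0 | 0.10 × 2/6 × 1.0 = 0.03 |
| 20% | 3 | 1.0 | 0.20 × 3/6 × 1.0 = 0.10 |
| 30% | 2 | 1.5 | 0.30 × 4/6 × 1.5 = 0.30 |

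Wider assumptions widen the range: 0.10 × 2/6 × 0.5 = 0.02 at one end and 0.50 × 4/6 × 2.0 = 0.67 at the other.

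**Single patient.** Three months off binder at 6.9 and three on binder at 5.4 give (3 × 6.9 + 3 × 5.4)/6 = 6.15 mg/dl. If ferric citrate simply holds 5.4, the mean falls by 6.15 − 5.40 = 0.75 mg/dl although nothing changed at the switch.

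**Control rate.** Section 10.1 does not say whether control is scored on each patient's six-month mean or month by month.
- Scored on the mean, this patient moves from uncontrolled to controlled.
- Scored by month, the patient moves from 3 of 6 months controlled to 6 of 6.

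The upper limit for the group, reached only if every affected patient or month crosses 5.5, is f under the first rule and f × (6 − m)/6 under the second. For the three cases above that is 10, 20 and 30 percentage points, or 3.3, 10 and 20.

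**Does the phosphorus ceiling prevent this?** No. A patient at 5.0 on binder with three off-binder months stays below a six-month mean of 8.0 as long as the off-binder months average less than (6 × 8.0 − 3 × 5.0)/3 = 11.0 mg/dl.

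**Possible offset in the 'after' period.** Section 7.1 provides two-weekly laboratory checks and titration over the first 2 months. If those months ran e mg/dl above the later level in all patients, the 'after' mean would rise by (2/6) × e. To cancel the 0.10 case completely, e would have to be 0.30 mg/dl. A smaller excess cancels part of it. The documents give no value for e.

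**The case against.** The strongest reply is that the size is entirely assumed and the low case is negligible. This stands: f, m and d appear nowhere in the documents. Entry also relies on six months of routine dialysis laboratory means, which suggests established dialysis patients. That is evidence of dialysis records, though, not of binder use throughout the window.

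A reader might infer that the bias can only favour ferric citrate. The documents do not support that. A dose cut inside the window leaves earlier months at a higher dose and lower phosphorus. A dose raised because phosphorus had just climbed can leave lower values early in the window. The 'after' period appears to include titration. Off-binder months are the clearest case, and for them the expected direction favours ferric citrate, but the net direction is not certain.

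A reader might also infer that secondary endpoint 10.2 iii is tilted the same way. It names no six-month window and refers to pill burden with the binder. If zero-pill months were averaged in, the earlier burden would look smaller and ferric citrate would compare worse.

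It can also be said that this is a feasibility pilot, not powered for significance, and that a fixed look-back is a legitimate descriptive choice. The first part rules out any claim about error rates, since no test is planned. It does not remove a shift in the reported mean and control rate. The second part is a reason to keep the six-month version in the report.

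Finally, trimming the 'before' months while keeping titration months in the 'after' period is not symmetrical. That is a fair caution, and it supports showing both versions.

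**Conclusion.** The gap is real. Entry is on current use, the comparator is a fixed six months, and no rule links the two. As written, 10.1 counts months with no binder as previous-binder control for anyone who started inside the window. The expected effect is a higher 'before' phosphorus and a lower 'before' control rate, to the advantage of ferric citrate.

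The size is unknown. It is about 0.03 to 0.30 mg/dl if 10% to 30% of patients have only 4 to 2 binder months and starting a binder lowers phosphorus by 1.0 to 1.5 mg/dl. Dose cuts in the window and titration after the switch may partly offset it. Confidence is high that the rule is missing. Whether the resulting bias is large enough to matter can be judged only from the binder record.

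**What to change.** In 10.1, define the 'before' mean and control rate over those months of the six-month window in which the 9.1.2 record shows the patient on a listed binder. Say which list counts, because the Protocol Summary includes aluminum and 5.1.1 does not. Report the full six-month version alongside.

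Add a sensitivity analysis limited to months at the enrollment binder and dose. The main definition does not deal with rises or cuts among patients already on a binder, and this analysis does.

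Report how many patients and how many months are affected. Do not exclude patients by a minimum number of on-binder months: any such cut-off would be arbitrary and would shrink a group of 55. A patient with no on-binder value in the window would appear in the full six-month version and be counted as such.

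For 10.2 iii, state only that previous pill burden is averaged over on-binder months.

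This changes endpoint wording and needs no new data, visits or change in treatment. The cost is fewer 'before' values, and so less precise ones, for some patients.
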